Appendix A – Instructions for Use

This appendix provides a copy of the Instructions for Use for the CARILLON Mitral Contour System.

Appendix B – Sample of Informed Consent

This appendix provides a copy of the sample informed consent for the REDUCE FMR Trial.

Appendix C – Subject Study Calendar

Schedule of assessments:

PRIMARY STUDY
(Treatment & Control pts)

CROSS-OVER REGISTRY
(Control pts upon primary study completion)

Study Task	Screening / Baseline	Index Procedure	Discharge	1 Month (±7 Days)	6 month (±14 Days)	12 month (±30 Days)	Screening / Baseline	CARILLON Procedure	Discharge	1 month (±7 Days)
							X	X	X	X
Informed Consent	X						X			
Inclusion/Exclusion Criteria	X						X			
Past Medical History & Physical Exam	X						X ^{11,12}			
Serum Pregnancy Test	X						X			
TEE ¹	X						X			
Coronary Angiography	X ²	X ²					X	X		
Coronary Sinus Venogram	X						X			
Intraprocedure Echo (TTE or TEE)		X						X		
Physical Exam			X	X	X	X			X	X
Vital Signs ³	X	X	X	X	X	X	X	X	X	X
Coagulation Tests ⁴	X						X			
Cardiac Enzymes ⁵	X		X	X	X	X	X		X	X
Chemistries ⁶	X		X	X	X	X	X ¹²		X	X
CBC ⁷	X		X	X	X	X	X ¹²		X	X
12-Lead ECG	X		X	X	X	X	X ¹²		X	X
Complete TTE	X			X	X	X	X ¹²			X
Exercise TTE ⁸	X			X	X	X	X ¹²			X
Abbreviated TTE ⁹ (safety)			X						X	
CXR or cine fluoroscopy			X		X	X			X	
Six Minute Walk Test	X ¹⁰			X	X	X	X ¹²			X
NYHA Classification	X			X	X	X	X ¹²			X
KCCQ	X			X	X	X	X ¹²			X
SF-12 QoL	X			X	X	X	X ¹²			X
Concomitant Medications	X	X	X	X	X	X	X	X	X	X
Adverse Events	X	X	X	X	X	X	X	X	X	X

- To rule out LAA clot - only required for subjects with a prior history of atrial fibrillation
- The eligibility angiography may occur immediately prior to randomization, unless a recent angiogram (see section 3.4.3.2) indicating no CAD requiring intervention is available. All Treatment group subjects undergo coronary angiography as part of the CARILLON Mitral Contour System procedure.
- Vital signs include: Blood pressure, heart rate, respiratory rate, oxygen saturation, temperature (degrees Celsius), weight, height (baseline only).
- Coagulation Tests include: PTT and Prothrombin time.
- Cardiac enzymes: cardiac troponin (cTn).
- Serum chemistries: sodium, potassium, chloride, BUN, creatinine and NT-BNP.
- CBC with differential: hemoglobin, hematocrit, platelets, and WBC.
- Exercise TTE will be done only at pre-identified qualified sites with supine bicycle ergometry.
- Abbreviated TTE safety assessment to rule out pericardial effusion.
- Six-minute walk test will be undertaken for screening and baseline (reference Appendix F: Six Minute Walk Test Protocol).
- No past medical history needed, physical exam only.
- Data from 12-mo follow-up of the primary study may be used if assessments were performed within 45 days to scheduled Cross-Over CARILLON procedure.

Appendix D – NYHA Classification of Patients with Diseases of the Heart

Functional Classification

- | | |
|-----------|---|
| Class I | Patient with cardiac disease but without resulting limitations of physical activity. Ordinary physical activity does not cause undue fatigue, palpitation, dyspnea, or anginal pain. |
| Class II | Patients with cardiac disease resulting in slight limitation of physical activity. They are comfortable at rest. Ordinary physical activity results in fatigue, palpitation, dyspnea, or anginal pain. |
| Class III | Patients with cardiac disease resulting in marked limitation of physical activity. They are comfortable at rest. Less than ordinary physical activity causes fatigue, palpitation, dyspnea, or anginal pain. |
| Class IV | Patients with cardiac disease resulting in inability to carry on any physical activity without discomfort. Symptoms of cardiac insufficiency or of the anginal syndrome may be present even at rest. If any physical activity is undertaken, discomfort is increased. |
-

(New York Heart Association Criteria Committee: Diseases of the Heart and Blood Vessels: Nomenclature and Criteria for Diagnosis, 6th ed. Boston, Little, Brown, & Co. 1964)

Appendix E – Echocardiogram Protocol

This appendix provides a copy of the Echocardiogram Protocol for the baseline, procedure, discharge, and follow-up echocardiograms for the REDUCE FMR Trial.

Appendix F – Six Minute Walk Test Protocol

All study subjects will perform a Six Minute Walk Test (6MWT) at screening, baseline and at each scheduled follow-up visit. To minimize any training effect, the screening and baseline tests should be two distinct assessments. Site personnel who administer the 6MWT will be blinded to the study subject's randomization assignment.

The test will be supervised by the Investigator or designee who will be responsible for the quality of patient preparation, reports and data collection.

- Prior to the start of each exercise test, make sure that the subject has not had any unstable cardiac symptoms and that there is no contraindication for proceeding with a stress test.
- Select a low-traffic corridor that is at least 25 meters in length. This corridor must not have any doors or obstructions that would open into the course and interfere with the subject's ability to walk. Mark off sections that are five (5) meters apart.
- Have a chair available for the study subject to rest in if needed.

Six Minute Walk Test Procedure

1 Study Subject Instructions

Instruct the study subject to walk as far as they can for six minutes. If they need to stop for fatigue or other medical reasons, they may do so, but should start walking as soon as they are able or are instructed to stop. Inform the subject to turn around when they reach the 25 meter mark and walk back to the starting point. They are to repeat this process as many times as they are able until they are instructed to stop. Answer any questions the subject has regarding the 6MWT prior to starting the test.

2 Exercise

As soon as the study subject starts walking, start the stop watch and monitor the distance covered. During the test, DO NOT speak with the subject unless there is an emergent reason.

3 Immediate Post Exercise

At six minutes, instruct the subject to stop and stand in that spot. Bring the chair to the subject and ask him or her to rest. Calculate the total distance walked during the six minutes to the nearest meter.

Appendix G – Definition of Stable Heart Failure Regimen

All study subjects must be on a stable heart failure medical regimen. A stable regimen is defined as the following:

- On an adjustable diuretic dose for three (3) months
- On ACE inhibitor or angiotensin receptor blocker for three (3) months with stable dosage for two (2) months (or documented intolerance to the medication)
- On a beta-blocker for three (3) months with stable dosage for two (2) months (or documented intolerance to the medication)

Patients must meet all three of the medication criteria unless intolerance to the medications is documented.

Appendix H – Exercise Echocardiography Protocol Synopsis

Only study centers with the necessary exercise equipment and echocardiographers experienced in obtaining echo imaging during exercise will be allowed to undertake exercise TTE assessments.

Study subjects who are physically capable of exercising on a supine bicycle ergometer and who consent to undergoing exercise echocardiography will undertake these assessments at baseline and at each scheduled follow-up visit.

The assessment will be supervised by the Investigator or qualified designee who will be responsible for the safety of the subject during the exercise protocol, quality of patient preparation, reports and data collection.

- Prior to the start of each exercise test, make sure that the subject has not had any unstable cardiac symptoms and that there is no contraindication for proceeding with the exercise test.

Exercise Methodology

Resting echo measurements will be obtained as part of the complete TTE assessment undertaken in the primary study protocol. Subjects will then undergo a graded exercise test on a supine bicycle ergometer with workloads being increased by 25W every 3 minutes until patient/symptom limitation.

Single-lead electrocardiograms and blood pressure will be recorded every minute. Subjects will be asked to declare their perceived exertion according to a Borg scale during the test.

Criteria to halt the test will be chest pain, severe dyspnea, severe fatigue, sustained hypotension, sustained ventricular tachycardia, short runs of three or more ventricular premature contractions, pallor, or dizziness.

Echocardiographic Acquisition Methodology

All echocardiographic images will be obtained in the last 90 seconds of each 3-minute workload level. Imaging should be acquired during a breath hold at the end of expiration. The averages of three consecutive beats during exercise will be used for each parameter.

Imaging views to assess the following parameters will be acquired:

- Effective Regurgitant Orifice Area
- Mitral Annular diameter/area measurements
- Pulmonary artery systolic pressure (from TR velocity)

References

- ¹ Lloyd-Jones D, Adams R, Carnethon M, et al. Heart disease and stroke statistics -- 2009 update: a report from the American Heart Association Statistics Committee and Stroke Statistics Subcommittee. *Circulation*. 2009;119:e21-e181.

### LIST OF ABBREVIATIONS AND DEFINITION OF TERMS

AT	As Treated
CAD	Coronary Artery Disease
CBC	Complete Blood Count
CI	Confidence Interval
GCV	Great Cardiac Vein
CMCS	CARILLON Mitral Contour System®
CO	Cardiac Output
CRT	Cardiac Resynchronization Therapy
CS	Coronary Sinus
CXR (PA)	Chest X-Ray (Posteroanterior)
ECG	Electrocardiography
EROA	Effective Regurgitant Orifice Area
FMR	Functional Mitral Regurgitation
HF	Heart Failure
ITT	Intent-to-Treat
KCCQ	Kansas City Cardiomyopathy Questionnaire
LAA	Left Atrial Area
LOCF	Last observation carried forward
LVEF	Left Ventricular Ejection Fraction
LVEDD	Left Ventricular End Diastolic Diameter
LVESD	Left Ventricular End Systolic Diameter
MRJA	Mitral Regurgitation Jet Area
NT-BNP	N-Terminal prohormone of Brain Natriuretic Peptide
NYHA	New York Heart Association
PP	Per protocol
QoL	Quality of Life
SAE	Serious Adverse Events
SAP	Statistical Analysis Plan

## STATISTICAL ANALYSIS PLAN

REDUCE\_FMR - SAP\_V2  
2018\_08\_06\_CT

REDUCE FMR Trial

Page 8/22

SF-12	Survey Form (12 questions)
TEE	Transesophageal Echocardiogram
TTE	Transthoracic Echocardiography
VC	Vena Contracta

## 1. OVERVIEW

This statistical analysis plan (SAP) describes the planned statistical analyses of the data collected in the course of the REDUCE FMR Trial: Safety and Efficacy of the CARILLON Mitral Contour System® in Reducing Functional Mitral Regurgitation (FMR) Associated with Heart Failure (HF).

This SAP provides additional details concerning the statistical analyses outlined in the protocol (Revision AA dated 27 October 2014). The purpose of the SAP is to ensure the credibility of the study findings by pre-specifying the statistical approaches to the analysis of study data.

### 1.1. Study Objective

The objective of this prospective, multi-center, randomized, double-blind trial is to assess the safety and efficacy of the CARILLON Mitral Contour System® (CMCS) in treating functional mitral regurgitation associated with Heart Failure (HF), compared to a randomized Control group which is medically managed according to HF guidelines.

### 1.2. Study Design

The REDUCE FMR Trial is a prospective, multi-center, randomized, double-blind clinical trial.

Subjects will be randomized between the Treatment Group and a Control Group. Subjects will be randomized in a 3:1 ratio (Treatment : Control). The Treatment group will be implanted with the CARILLON device. The Control group will be medically managed according to current HF guidelines.

As this is a double-blinded study, both the patients (Treatment and Control groups) and the assessors of the primary endpoint will be blinded for twelve months.

Subjects randomized to the Control or Treatment group will have safety and efficacy assessments performed at baseline, one (1), six (6), and twelve (12) months after randomization.

Subjects randomized to the Control group may be offered the CARILLON device once they have completed the protocol defined follow-up period (Cross-Over Registry).

### 1.3. Study Plan

#### 1.3.1. Study population

Consent up to 180 subjects suffering from HF and presenting with FMR from up to 20 centers in Australia and Europe in order to randomize up to 120 subjects.

#### 1.3.2. Study Device

The CARILLON Mitral Contour System® (XE2) is a Class III medical device and is manufactured by Cardiac Dimensions, Inc., in Kirkland, Washington, USA. The device received CE-Mark on 3rd August 2011. In Australia, the CARILLON device is intended "For Clinical Trial Use Only".

The CMCS (XE2) consists of the following components:

- An implant intended for permanent placement in the coronary sinus (CS)/great cardiac vein (GCV);
- A delivery system which consists of a custom 9F delivery catheter and a handle assembly.

The implant is attached to the handle assembly and is delivered through the delivery catheter to the coronary vein along the posterolateral aspect of the mitral annulus.

The CMCS is indicated for use in patients with secondary (functional) mitral regurgitation.

The CMCS is contraindicated for use in:

- Patients with existing devices in the CS/GCV;

## CONFIDENTIEL / CONFIDENTIAL

- Patients who have had a mitral valve replacement or a mitral annuloplasty ring implant.

### 1.3.3. Randomization

Randomization will occur in a 3:1 allocation to the Treatment (CARILLON) or Control group. Randomization has been stratified according to investigational center in a randomized permuted blocks design.

After all pre-randomization assessments are completed, each subject will be assigned sequentially to one of the two study groups (Treatment or Control), by means of a computer-generated random number scheme created by the Sponsor. The study coordinator and limited study personnel (e.g., implanting physician) will have also knowledge of the treatment assignment.

For subjects randomized to the Treatment group, the CMCS procedure will be performed.

### 1.3.4. Blinding

Subjects randomized to the Control group will experience an index procedure similar to the Treatment group, however, without device placement. To ensure that subjects randomized to the Control group will not be able to deduce the treatment assignment based on the type of intervention or time associated with the procedure, minimal interventional procedures, such as femoral arterial pressure monitoring and a jugular venous drip. If a recent (within the last 3 months for ischemic cardiomyopathy or 12 months for non-ischemic cardiomyopathy) coronary angiogram is available, this assessment may be precluded.

This will be a double-blind study in order to reduce the effect of bias and potential placebo effect on specific primary and/or secondary endpoint assessments. All study subjects and any study personnel responsible for primary efficacy and/or select secondary endpoint assessments will be blinded as to whether subjects are in the Treatment group or the Control group. Blinding will be maintained through the 12 month follow-up. All study personnel will be trained to follow study blinding procedures to ensure maintenance of the study blind. Subjects will be continually reminded that adhering to the blinding procedures is a critical part of their involvement in the study.

The assessors of the NYHA Class, six-minute walk test, echo corelab assessors, and Quality of Life Questionnaires (Kansas City Cardiomyopathy Questionnaire and SF-12) will not be aware of the treatment assignment.

### 1.3.5. Unblinding

The treatment assignment for a subject will be unblinded only in the following circumstances:

- 1) In the event of medical emergency where it is medically necessary to know if the subject received an implant
- 2) After all randomized study subjects have completed their 12-month visits, the treatment assignment will be unblinded for statistical analysis in readiness for submission to regulatory authorities

The DSMB and/or CEC, upon request, may be provided with the randomization assignment of a particular subject(s) or to assess safety trends between study groups. This can be provided by the study statistician and does not require unblinding of critical site and study personnel.

### 1.3.6. Patient's Follow-up

Subjects will be followed for 12 months from the time of randomization to meet primary and secondary endpoints in accordance with the follow-up periods.

## STATISTICAL ANALYSIS PLAN

REDUCE\_FMR - SAP\_V2  
2018\_08\_06\_CT

REDUCE FMR Trial

Page 11/22

6 visits are scheduled:

- Visit 1: Screening/Baseline\*;  
\*If 2 Screening/Baseline visits are performed for a patient the latest Screening/Baseline data will be considered for analyses.
- Visit 2: Index Procedure;
- Visit 3: Discharge;
- Visit 4: 1 Month Follow-up;
- Visit 5: 6 Months Follow-up;
- Visit 6: 12 Months Follow-up.

### 1.3.7. Study Assessments

The following flowchart applies to the study:

Study Task	Screening / Baseline		Index Procedure	Discharge	1 Month (±7 days)	6 Months (±14 days)	12 Months (±30 days)
Informed Consent	X	Randomization					
Inclusion/Exclusion Criteria	X						
Past Medical History & Physical Exam	X						
Serum Pregnancy Test	X						
TEE 	X						
Coronary Angiography	X 		X 				
Intraprocedure Echo (TTE or TEE)			X				
CHF Focused History & Physical Exam				X	X	X	X
Vital Signs	X		X	X	X	X	X
Coagulation Tests	X						
Cardiac Enzymes	X			X	X	X	X
Chemistries	X			X	X	X	X
CBC	X			X	X	X	X
12-Lead ECG	X			X	X	X	X
Complete TTE	X			X	X	X	

# STATISTICAL ANALYSIS PLAN

REDUCE\_FMR - SAP\_V2  
2018\_08\_06\_CT

REDUCE FMR Trial

Page 12/22

Study Task	Screening / Baseline		Index Procedure	Discharge	1 Month (±7 days)	6 Months (±14 days)	12 Months (±30 days)
Exercise TTE 	X				X	X	X
Abbreviated TTE  (safety)				X			
CXR (PA & Lateral) or cine fluoroscopy				X	X	X	X
Six Minute Walk Test	X 				X	X	X
NYHA Classification	X				X	X	X
KCCQ	X				X	X	X
SF-12 QoL	X				X	X	X
Concomitant Medications	X		X	X	X	X	X
Adverse Events	X		X	X	X	X	X

1. To rule out LAA clot - only required for subjects with a prior history of atrial fibrillation
2. The eligibility angiography may occur immediately prior to randomization, unless a recent angiogram indicating no CAD requiring intervention is available. All Treatment group subjects undergo coronary angiography as part of the CMCS procedure.
3. Exercise TTE will be done only at pre-identified qualified sites with supine bicycle ergometry.
4. Abbreviated TTE safety assessment to rule out pericardial effusion.
5. Six-minute walk test will be undertaken for screening and baseline.

## 2. STATISTICAL METHODS

### 2.1. General Statistical Considerations

#### 2.1.1. Handling Missing Data

If any subject does not have endpoint data available (12-month data), the primary analysis will assume that data as missing and that subject's data will not be included in the primary analysis.

Missing data will be imputed for all missing primary, secondary and observational endpoint parameters using a last observation carried forward (LOCF) methodology and will be presented as a sensitivity analysis to assess the robustness of results.

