The clinical relevance of this magnitude of a difference is supported by other trials evaluating the clinical impact of functional mitral regurgitation. For example, Amigoni showed in the VALIANT trial database that a 1% increase in FMR was associated with an increased risk of heart failure hospitalization, and an increased risk of death or heart failure hospitalization.³² Extending the clinical significance to mortality, Grigioni showed in a group of patients with Q-wave MI that those patients with a regurgitant volume >30 ml demonstrated higher mortality than those regurgitant volume <30 ml (RR 1.13 per 10 ml RVol increase).³³ In CRT candidate patients with at least mild MR and an average LVEF $25 \pm 7\%$, Madaric showed that CRT decreased the regurgitant volume from 36 ± 19 ml to 25 ± 11 ml, but he also showed that even an increase in regurgitant volume from 25 ± 11 ml at rest to 29 ± 12 ml with exercise was statistically significant to $p < 0.001$.³⁴ Lastly, Bursi noted in their study of heart failure after myocardial infarction that patients with MR had worse outcomes, which exhibited a graded ‘dose-response’ relationship with the severity of MR, a pattern that supports causality.³⁵ These data taken together suggest that a small change in FMR (e.g., 1%) can be clinically significant, and the 10 ml difference between populations proposed in this study is similar to the magnitude of change seen in other trials, and is clinically relevant.

Data Analysis

The mean improvement in regurgitant volume for each treatment group, from baseline to twelve months, will be compared in a two-sided, two-sample t-test. The 95% confidence interval on the between-group difference will also be calculated and presented. If assumptions of normality are violated, the nonparametric Mann-Whitney test will be used to assess statistical significance, and the 95% confidence interval on the

difference between groups will be calculated using the Hodges-Lehmann estimate and distribution-free confidence interval based on a Wilcoxon Rank Sum test. The primary analysis will be conducted on the intent-to-treat population, and supportive analyses will be performed on the previously defined per-protocol and as-treated populations (reference Section 6.2: Study Analyses). Further supportive analyses will be conducted which characterize the longitudinal effect of treatment on regurgitant volume in a repeated measures regression model.

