6.7 Size and Duration of Trial

An estimated minimum of 76 randomized, evaluable subjects is required to have 80% power to detect a reduction in the change in regurgitant volume between CARILLON device and Control groups. A total of 120 subjects at up to 25 centers will be randomized, allowing for approximately 30% attrition (mortality, missing data and loss to follow-up) in the first 12 months of follow-up.

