### 2.1.3. Inferential Analysis

Data will be compared between the two groups using bilateral tests at the type I error 5% level.

- *Continuous variables*: the appropriate test will be chosen depending on the data distribution.  
The normality of quantitative data will be tested using the Shapiro-Wilk test.
  - if the normality test pvalue is > 0.05, the data will be considered as normally distributed and the Student test will be used.
  - else, the data will be considered as not normally distributed and the Wilcoxon Rank Sum test will be used.
- *Categorical variables*: the appropriate test will be chosen depending on the expected cell frequencies:
  - If all expected cell frequencies are  $\geq 5$  then the Chi test will be used.
  - Otherwise, the Fisher's exact test will be used.

The 95% confidence interval in regurgitant volume mean difference from baseline to 12 months will be presented by treatment group. If assumptions of normality are violated, the 95% confidence interval will be calculated using the Hodges-Lehmann estimate and distribution-free confidence interval based on a Wilcoxon Rank Sum test.

Further supportive analyses will be conducted which characterize the longitudinal effect of treatment on regurgitant volume in a repeated measures regression model, using a mixed effects model approach. Fixed effects will be treatment group and time effect. Site effect will be a random effect. Interaction between treatment group and site will also be studied.

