#### 2.3.2. Definition of patient populations

5 populations will be defined:

- The enrolled population will include all patients who consented to participate to the study.
- The screen failure population will include all enrolled patients who did not meet all eligibility criteria or randomized to treatment group but procedure discontinued before an implant attempt. Only a listing of these patients will be presented.
- The Intent-to-Treat (ITT) population will include all patients who fulfill all eligibility criteria and either underwent the procedure and on whom a device implant was attempted, or are considered as control patients.

This population will therefore include all randomized patients except the patients for whom the procedure was discontinued before an implant attempt (see Fig 1 below).

This population will be analyzed regardless of the treatment actually received: if there is an error in treatment (i.e. subject was not treated as randomized), the analysis will be performed according to the randomized group assignment, not the treatment actually received.

- The As -Treated (AT) population will include all ITT patients who left clinic with the randomized therapy administered (i.e., randomized to Treatment group and received a permanent implant, or randomized to Control group)

This population will therefore include all randomized patients except the patients who underwent the procedure but were not implanted (see Fig 1 below).

This population will be analyzed according to the treatment actually received: if there is an error in treatment (i.e. subject was not treated as randomized), the analysis will be performed according to the treatment actually received, not the randomized group assignment.

- The Per Protocol (PP) population will include all AT patients who received randomized therapy, assessors remained blinded, and who did not receive alternative or confounding therapies (e.g., CRT therapy, transplant, stenting, etc.) through the primary endpoint timeframe of the study, who did not met any major deviation (see 2.3.3).

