### 2.4.6. Supportive Analyses

In addition, a series of supportive, sensitivity analyses will be performed to assess the robustness of the primary analysis results:

- Primary endpoint analysis on ITT population according to etiology of cardiomyopathy (ischemic vs. non-ischemic) through the primary endpoint.
- Primary and secondary efficacy endpoints analysis using LOCF methodology.
- Primary and secondary efficacy endpoints analysis by MR Grade or MR Grade grouping
- Primary and secondary efficacy endpoints analysis using associated baseline characteristics
- Primary endpoint analysis using qualitative measure imputation of core lab derived values where quantification is technically challenging
- Calculation of treatment effect using mitral regurgitation volume and MR grade as parameters in responders and non-responders
- Assessment of treatment effects according to other important clinical subgroups such as:
  - i. Atrial fibrillation vs normal sinus rhythm
  - ii. Baseline MR grade

MEDPASS

INTERNATIONAL

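### The primary analysis drops every patient without a 12-month value, and neither LOCF nor the supportive mixed model as listed can check the 12-month result

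*SAP*

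**What the plan says.** The primary test is a two-sided two-sample t-test, or a Wilcoxon test if normality fails, on change in regurgitant volume from baseline to 12 months (Protocol 6.6; SAP 2.4.2, Primary Endpoint). Both documents omit a patient who has no 12-month value: that subject's "data will not be included in the primary analysis" (SAP 2.1.1; same rule in Protocol 6.2). Protocol 6.7 sets 120 randomized patients, "allowing for approximately 30% attrition (mortality, missing data and loss to follow-up) in the first 12 months of follow-up".

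For missing values, SAP 2.1.1 says: "Missing data will be imputed for all missing primary, secondary and observational endpoint parameters using a last observation carried forward (LOCF) methodology". Protocol 6.2 describes this as imputing the last value observed. SAP 2.4.6 adds "Primary endpoint analysis using qualitative measure imputation of core lab derived values where quantification is technically challenging", which concerns echoes that are hard to quantify and not patients who have left. It also adds "Primary and secondary efficacy endpoints analysis using associated baseline characteristics", which is not defined further.

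Protocol 6.6 promises a supportive analysis to "characterize the longitudinal effect of treatment on regurgitant volume in a repeated measures regression model". SAP 2.1.3 gives its terms: "Fixed effects will be treatment group and time effect. Site effect will be a random effect". A treatment-by-site interaction will also be studied. No treatment-by-visit term, baseline covariate or within-patient covariance is listed, and the SAP does not say whether baseline counts as one of the visits.

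SAP 2.3.2 says of its ITT set: "This population will therefore include all randomized patients except the patients for whom the procedure was discontinued before an implant attempt". Protocol 6.2 keeps all subjects in their randomized group, including Treatment patients without a permanent implant.

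**The concern.** A complete-case comparison is randomized only in name once a substantial share of patients has left, and mortality is counted within the 30%. The reader then depends on the sensitivity analyses to judge whether the 12-month result is sound. Here one check carries forward values from visits where the effect may differ. The other estimates a different quantity. Neither addresses loss that depends on the unseen outcome, and neither says what the estimate means for patients who died.

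The primary test also leaves information unused. Baseline is subtracted but is not a covariate, and the resting echoes scheduled at 1 and 6 months (Protocol 3.8.1 and 3.8.2) play no part in it.

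**Working it through.** **Inputs from the documents:** difference -10 ml (-12.4 against -2.4), SD of change 13 ml, two-sided 0.05, 3:1 allocation, 120 randomized (90:30), about 30% attrition. **Assumed, because the documents do not give them:** loss spread evenly over the three between-visit intervals (10% of patients in each), the correlations between visits, and the dropout mechanisms.

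1. *The plan's own figure.* Noncentral-t power is 79.6% at 54:18 and 81.8% at 57:19, so 76 is the smallest 3:1 total that reaches 80%. The stated 76 is reproduced.

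2. *Power after attrition.* 120 × 0.70 = 84 (63:21). SE = 13 × √(1/63 + 1/21) = 3.28, and power is 85.5%.

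3. *Value of a baseline covariate.* With equal variances and baseline-to-12-month correlation r, adjustment multiplies the variance of the change-score comparison by (1 + r)/2. At 63:21:

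| r | factor | power |
|---|---|---|
| 0.4 | 0.70 | 95.0% |
| 0.5 | 0.75 | 93.6% |
| 0.6 | 0.80 | 92.1% |
| 0.8 | 0.90 | 88.9% |
| 0.9 | 0.95 | 87.2% |

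4. *LOCF under purely random loss, constant effect of -10 ml.* The 10% lost before 1 month carry baseline and contribute zero change in both arms: 0.90 × (-10) = -9.0. Simulation gives -8.9 to -9.1. If the effect grows (-4, -7, -10): 0.10 × 0 + 0.10 × (-4) + 0.10 × (-7) + 0.70 × (-10) = -8.1.

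5. *The supportive model as listed.* With one treatment coefficient, the estimate is a weighted mean of the visit-specific effects. Weighting only by patients present (0.90, 0.80, 0.70), a fading effect (-14, -12, -10) gives -(12.6 + 9.6 + 7.0)/2.4 = -12.2. A growing effect (-4, -7, -10) gives -(3.6 + 5.6 + 7.0)/2.4 = -6.75. Likelihood weighting of post-baseline visits gives -12.3 and -6.6. It gives -10.0 only when the effect is constant.

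6. *Dropout bias.* The true 12-month difference is -10 ml, with 30% lost, correlation 0.5 with baseline and 0.7 between later visits, and dropout log-odds of 0.5, 1 or -1 per SD. The last column is a model of all visits with treatment-by-visit terms.

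| Dropout depends on | t-test | completer ANCOVA | all-visit model |
|---|---|---|---|
| same rule in both arms, equal loss | within about 0.15 of -10 | within about 0.15 of -10 | – |
| one arm, last observed level | -9.9 to -10.1 | -8.6 to -11.4 | -9.9 to -10.1 |
| one arm, last observed change | -8.2 to -11.8 | -8.8 to -11.1 | – |
| one arm, current unobserved level | -8.9 to -11.3 | -7.8 to -12.3 | -8.6 to -11.5 |

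A dash means that no figure is reported. LOCF with baseline carried gives about -8.9 in the first row. The first row needs equal loss as well as the same dependence. In a separate simulation, one rule on the last change was applied to both arms, and the treatment effect itself made loss unequal (25-34% Treatment, 42-43% Control). The completer difference was then -8.7 to -9.3, against -9.8 to -10.0 with full data; a treatment-by-visit model gave -9.6 to -9.9.

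7. *What a delta analysis would show.* With 27 of 90 Treatment values missing, each 1 ml shift in the imputed values moves the estimate by 27/90 = 0.30 ml. Taking an all-visit SE of 2.74 (2.60-2.90 over the correlations tried), an estimate of -10 loses significance at a shift of (10 - 1.99 × 2.74)/0.30 = 15.2 ml. An estimate of -7 does so at (7 - 1.99 × 2.74)/0.30 = 5.2 ml.

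**The case against.** The strongest reply is that the plan is adequate as it stands. Power exceeds 80% after the full allowance. Patients and endpoint assessors are blinded, which makes similar dropout in the two arms plausible, and with equal loss the t-test is then nearly unbiased. Exit reasons by group (SAP 2.4.1.1), counts of missing values (SAP 2.1.2) and mortality by arm (SAP 2.4.5) are already to be reported. The protocol's reference to a longitudinal effect may intend a treatment-by-time term, and the undefined SAP 2.4.6 analysis with baseline characteristics may be a baseline adjustment. The precision gain also shrinks at high correlation, to about 2 points of power at 0.9.

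All of this stands, and it limits the point. It does not supply a 12-month check: an intended interaction must be written into the SAP to count as pre-specified, and LOCF is off target even in the benign case.

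Several stronger readings are tempting but unsupported:

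- *The trial is underpowered.* It is not, on its own assumptions.
- *The primary estimate is biased in a known direction.* The table shows both directions, and near-zero bias in some cases.
- *Baseline is ignored.* It is subtracted.
- *Completer ANCOVA is safer, or riskier, than the t-test.* The ranking reverses between dropout on level and dropout on change.
- *The supportive model inflates type I error.* That would require treating a patient's visits as independent, and the repeated-measures label points the other way.
- *The ITT definition inflates the effect by an amount bounded by the 15% in Protocol 6.6.* That 15% refers to Non-Implanted patients. Protocol 3.7.2 defines them as attempted and followed to 12 months, and SAP 2.3.2 keeps them in ITT. No rate is given for patients with no attempt.

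**Conclusion.** The point holds as a weakness in the planned checks and an avoidable loss of precision. It does not show that the primary test is wrong. If the allowed attrition occurs, 36 of 120 randomized patients leave the primary comparison, deaths among them. LOCF is the only method named for those lost before 12 months. It sits about 1 ml from a true -10 ml under random loss or equal, like-for-like dropout, given a constant effect and 10% lost before the first follow-up echo. Carrying baseline is the natural reading of Protocol 6.2. The listed mixed model misses a 12-month effect of -10 ml by about 2.3 to 3.4 ml if the effect fades or grows as assumed.

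One-arm dropout put the primary t-test between about -8 and -12 ml in the scenarios run. These are illustrations and not bounds, and no method tried is safe when loss depends on the unseen value.

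The difference between the SAP and protocol ITT definitions is real. Reconciling it alone does not move the estimate, because Protocol 3.7.1.2 exits the no-attempt patients after a 1-month safety assessment without a 12-month echo.

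**What to change.** (a) In SAP 2.1.3, specify the planned mixed model fully: regurgitant volume at 1, 6 and 12 months as outcome; treatment, visit, treatment-by-visit, baseline and baseline-by-visit as fixed effects; unstructured within-patient covariance. Report the 12-month contrast. This adjusts for baseline and uses partial follow-up. Making it the primary analysis is optional. The case for that is precision, and it would need a protocol amendment with ethics and regulatory review (Protocol 7.5).

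(b) In SAP 2.1.1 and 2.4.6, add multiple imputation under missing-at-random with a delta (tipping-point) analysis, beside LOCF or in its place. Removing LOCF from Protocol 6.2 and 6.9 would also need an amendment; adding the new analyses beside it is SAP wording. Treat deaths explicitly: either state that the estimate applies to survivors and show mortality by arm next to it, or add a rank analysis with deaths ranked worst.

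(c) Reconcile the ITT definition in SAP 2.3.2 with Protocol 6.2. State that this changes the estimate only if patients with no implant attempt are imputed.

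The cost is modest programming, plus reliance on a model and a missing-at-random assumption. The delta analysis shows how far the conclusion depends on that assumption.
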